6.2 IMPORTANT PROTOCOL VIOLATIONS

[Table 6.2: 1](#) defines the different categories of important protocol violations (IPVs) to be considered for evaluability of efficacy (E) or for patients’ right and safety (S). IPVs marked with an ‘S’ only will not lead to exclusion of a patient from the per-protocol-set (PPS). Only the IPVs marked with ‘E’ will lead to exclusion from the PPS.

16.1.9 Documentation of statistical methods

Proprietary confidential information © 2019 Boehringer Ingelheim International GmbH or one or more of its affiliated companies

Proprietary confidential information © 2019 Boehringer Ingelheim International GmbH or one or more of its affiliated companies

Table 6.2: 1 Important protocol violations

| PV Category / Code | Description | Criterion to check for PV (Comments) | Efficacy (E) or Safety (S) | PV Leading to Exclusion from PPS | |
|--------------------|------------------------------------|--|--|----------------------------------|-----|
| A | Entrance criteria not met | | | | |
| A1 | Target indication not met | | | | |
| | A1.1 | No type 2 diabetes | Inclusion criterion #1 checked NO | E | Yes |
| | A1.2 | Antidiabetic background therapy not as required | Inclusion criterion #2 checked NO or required antidiabetic background not recorded on eCRF | E | Yes |
| A2 | Inclusion criteria violated | | | | |
| | A2.1 | HbA _{1c} out of range at start of placebo run-in period | Inclusion criteria #3 not met and/or HbA _{1c} at Visit 1 out of range for inclusion by >0.2% (i.e., <7.3% or >10.2%) | E | Yes |
| | A2.2 | Age out of range at screening | Inclusion criteria #4 not met and/or Age < 18 years | E | Yes |
| | A2.3 | Body mass index (BMI) out of range at screening | Inclusion criteria #5 not met and/or BMI > 45 kg/m ² | E | Yes |
| A3 | Exclusion criteria violated | | | | |
| | A3.1 | Treatment with protocol excluded antidiabetic drugs | Exclusion criterion #2, #5 checked Or Intake of any of the excluded drugs reported on the eCRF within the time prior to informed consent specified in the exclusion criteria | E | Yes |
| | A3.2 | Relevant concomitant diagnoses | Exclusion criterion #3 checked Or acute coronary syndrome (non-STEMI, STEMI and unstable angina pectoris), stroke or TIA recorded on concomitant diagnoses eCRF within previous 3 months | S | No |
| | A3.3 | Impaired hepatic function | Exclusion criterion #4 checked Or ALT (SGPT) or AST (SGOT) or alkaline phosphatase > 3xULN at screening / run-in phase | S | No |
| | A3.4 | Gastrointestinal surgery | Exclusion criterion #6 checked | E | Yes |

16.1.9 Documentation of statistical methods

Proprietary confidential information © 2019 Boehringer Ingelheim International GmbH or one or more of its affiliated companies

Proprietary confidential information © 2019 Boehringer Ingelheim International GmbH or one or more of its affiliated companies

Table 6.2: 1 (continued) Important protocol violations

| PV Category / Code | Description | Criterion to check for PV (Comments) | Efficacy (E) or Safety (S) | PV Leading to Exclusion from PPS |
|--------------------|---|---|----------------------------|----------------------------------|
| A3.5 | Medical history of cancer (except for basal cell carcinoma) and/or treatment for cancer within the last 5 years | Exclusion criterion #7 checked | S | No |
| A3.6 | Blood dyscrasias or relevant disorders | Exclusion criterion #8 checked | S | No |
| A3.7 | Known hypersensitivity to any of the drugs in the study regimen | Exclusion criterion #9 checked | E | Yes |
| A3.8 | Treatment with protocol excluded anti-obesity drugs | Exclusion criterion #10 checked Or intake of any of the excluded drugs reported on the eCRF within the time prior to informed consent specified in the exclusion criterion | E | Yes |
| A3.9 | Treatment with protocol excluded systemic steroids or change in thyroid hormone dose | Exclusion criterion #11 checked Or intake of any of excluded drugs reported on the eCRF within the time prior to informed consent specified in the exclusion criteria | E | Yes |
| A3.10 | Specific exclusion criterion for pre-menopausal women violated | Exclusion criterion #12 checked | S | No |
| A3.11 | Alcohol or drug abuse that may interfere with study participation | Exclusion criterion #13 checked | E | Yes |
| A3.12 | Participation in another trial with an investigational drug within 2 months prior to informed consent | Exclusion criterion #14 checked Final decision at the DBL meeting (medical judgement), depending on the type of drug given in the prior trial (only if investigational drug interferes with glucose metabolism). | E | Yes |

16.1.9 Documentation of statistical methods

Proprietary confidential information © 2019 Boehringer Ingelheim International GmbH or one or more of its affiliated companies

Boehringer Ingelheim

TSAP for BI Trial No: 1218.102

Proprietary confidential information © 2019 Boehringer Ingelheim International GmbH or one or more of its affiliated companies

Table 6.2: 1 (continued) Important protocol violations

| PV Category / Code | Description | Criterion to check for PV (Comments) | Efficacy (E) or Safety (S) | PV Leading to Exclusion from PPS |
|--------------------|---|---|----------------------------|----------------------------------|
| B | Informed consent | | | |
| B1 | Informed consent not available | Date of informed consent missing Or No signature on patient's "Declaration of Informed Consent" Patient's data will not be used at all. | S/E | Yes |
| B2 | Informed consent too late | Date of informed consent not obtained prior to any study related procedure or re-consent with new version of informed consent too late. Minimum requirement for initial informed consent <= date of Visit 1/date of any study procedure | S | No |
| C | Trial medication and randomisation | | | |
| C1 | Incorrect trial medication taken | | | |
| C1.1 | No study medication taken | Patient randomised but no study medication taken. Exclude also from FAS and TS. | E | Yes |
| C1.2 | Incorrect trial medication taken | Wrong medication taken (different medication than the patient was randomised to taken at any visit, i.e. drug kit recorded in eCRF from different treatment group than drug kit assigned by IVRS) Can only be finally judged after DBL since unblinding information is required. | E | Yes |
| C2 | Randomisation not followed | | | |
| C2.1 | Treated without randomisation | Patient treated according to eCRF but not randomised by IVRS. Exclude also from FAS and RS. | E | Yes |
| C3 | Non-compliance | | | |
| C3.1 | Non-compliance with drug intake | Gross non-compliance issues only – based on compliance section of CRF (at least two times on treatment compliance was outside 80-120% according to eCRF) Final decision at the DBL meeting. (medical judgement) | E | Yes |

16.1.9 Documentation of statistical methods

Proprietary confidential information © 2019 Boehringer Ingelheim International GmbH or one or more of its affiliated companies

Proprietary confidential information © 2019 Boehringer Ingelheim International GmbH or one or more of its affiliated companies

Table 6.2: 1 (continued) Important protocol violations

| PV Category / Code | Description | Criterion to check for PV (Comments) | Efficacy (E) or Safety (S) | PV Leading to Exclusion from PPS | |
|--------------------|-------------|--|--|----------------------------------|-----|
| | C3.2 | Non-compliance with criteria for removal from the trial | Criteria for removing a patient from the trial not adhered to. Final decision at the DBL meeting. (medical judgement) | E | Yes |
| | C3.3 | Treatment interruption for more than 10 consecutive days | Documented treatment interruption for 11 consecutive days or more. | E | Yes |
| C4 | | Medication code broken | | | |
| | C4.1 | Medication code broken without just cause | Medication code was broken for no valid reason. Final decision at the DBL meeting. (medical judgement) | E | Yes |
| D | | Concomitant medication | | | |
| D1 | | Prohibited medication use | | | |
| | D1.1 | Rescue medication taken without just cause | Review of eCRF for use of rescue medication within the 24 weeks and fasting plasma glucose prior to rescue therapy < 90% of protocol requirement for rescue medication (if threshold is 240, FPG<216 mg/dL or <12 mmol/L prior to rescue medication) and no documented hyperglycaemia. | E | Yes |
| | D1.2 | Antidiabetic drug taken that is not a protocol defined rescue medication and criterion to administer rescue medication not fulfilled | Antidiabetic drug other than protocol defined rescue medication taken and criterion for rescue therapy as in D1.1 not fulfilled. | E | Yes |
| | D1.3 | Use of contraindicated drugs | Review of eCRF for contraindicated drugs. Final decision at the BRPM meeting. (medical judgement) | E | Yes |

Note : Missing visits, evaluations, and tests will be considered missing data, not protocol deviations.

6.3 PATIENT SETS ANALYSED

SCR - Screened Patients Set

It consists of all patients screened for the trial, with informed consent given and who completed at least some screening procedures at Visit 1.

RS - Randomised set

It consists of all patients from the screened set who were randomised to study drug, regardless of whether any study drug was taken.

TS - Treated Set

It consists of all patients treated with at least one dose of study drug. The TS is the basis for safety analyses.

FAS - Full Analysis Set

It consists of all patients randomised in the TS who had a baseline HbA1c value and at least one on-treatment HbA1c value. The FAS is the basis for the intention-to-treat (ITT) analysis.

FAS - Completers

It consists of all patients in the FAS with treatment duration no less than 149 days and did not prematurely discontinue the trial. The date of last intake of study drug should be on or after the start of the time window of the last on-treatment visit, and an HbA1c value should be available within the time window for this visit.

PPS - Per Protocol Set

It consists all patients in the FAS without important PVs for efficacy.

MTT-set - Meal Tolerance Test set

It consists all patients of the FAS with a valid MTT at baseline and at the end of the study. An MTT is considered valid if it has a valid FPG and a valid 2 hour PPG value.

Table 6.3: 1 Check-box for data set to be used for which class of endpoints

| Class of endpoint | TS | FAS | MTT-set |
|--|----|-----|---------|
| Primary endpoint –primary analysis | | X | |
| Primary endpoint –sensitivity analysis | | | |
| Other efficacy endpoints | | X | |
| MTT endpoints | | | X |
| Safety endpoints | X | | |
| Demographics | X | | |
| Baseline for efficacy | | X | |

6.5 POOLING OF CENTRES

This section is not applicable as no analysis by centre will be performed.

6.6 HANDLING OF MISSING DATA AND OUTLIERS

Based on the different reasons of patients' data missing for different endpoints, various methods will be used to assess the impact of missing data on the efficacy endpoints of this trial, depending upon the type of the endpoint. A description of the various approaches are given in the following:

Observed cases (OC)

One general approach that is possible for all endpoints is to analyse only the available data that were observed while patients were on treatment, i.e. excluding the missing data. Missing data in this analysis will not be replaced.

For all efficacy endpoints, this OC-technique will be adapted by setting any values taken after rescue medication to missing. The definition of rescue therapy please refers to [section 5.3](#).

It should be noted that this method provides unbiased estimates only under the assumption that the data are missing at random; and so, this method is likely to lead to anti-conservative estimates of the treatment effects in case of data missing due to patients dropping-out because of the lack of efficacy of the drug under study. However, since it can be expected that the drop-out rate due to lack of efficacy and the rate of patients with rescue therapy is higher in

16.1.9 Documentation of statistical methods

Proprietary confidential information © 2019 Boehringer Ingelheim International GmbH or one or more of its affiliated companies

Boehringer Ingelheim

TSAP for BI Trial No: 1218.102

Page 23 of 47

Proprietary confidential information © 2019 Boehringer Ingelheim International GmbH or one or more of its affiliated companies

the placebo group, this approach will lead to a conservative estimates of the placebo-adjusted treatment effect of linagliptin.

16.1.9 Documentation of statistical methods

Proprietary confidential information © 2019 Boehringer Ingelheim International GmbH or one or more of its affiliated companies

Proprietary confidential information © 2019 Boehringer Ingelheim International GmbH or one or more of its affiliated companies

Non-completers considered as failure (NCF)

For binary endpoints like a treat to target response of $HbA_{1c} < 7\%$ a conservative method to replace missing values is to consider them as “failure”. Missing data due to early discontinuation will be replaced as “failure” (e.g. $HbA_{1c} \geq 7\%$) up to the planned final visit to be reached by all patients. Similarly, values obtained after the start of rescue therapy will be considered “failure”.

For binary endpoints that are derived from quantitative endpoints (e.g. HbA_{1c}), missing values within a course of measurements on treatment will be replaced on the basis of the corresponding imputed values of underlying quantitative endpoint (e.g. based on imputation as described for HbA_{1c}).

16.1.9 Documentation of statistical methods

Proprietary confidential information © 2019 Boehringer Ingelheim International GmbH or one or more of its affiliated companies

Boehringer Ingelheim

TSAP for BI Trial No: 1218.102

Proprietary confidential information © 2019 Boehringer Ingelheim International GmbH or one or more of its affiliated companies

Table 6.6: 1 Summary of imputation methods for efficacy endpoints

| Imputation method | Endpoint | Handling of missing values | Handling of values after rescue therapy |
|-------------------|---|---|--|
| OC | Continuous and binary endpoints | No imputation | Excluded (considered missing). One picked value per visit. |
| NCF | Binary endpoints derived from continuous endpoints (e.g. HbA _{1c} <7.0%) | Missing values after premature discontinuation of study drug are considered failure (endpoint not achieved). Missing values with subsequent present on-treatment values will be imputed based on the interpolated values for the underlying continuous endpoint. | Values after the start of rescue therapy are imputed as failure. |

Safety and other variables

Missing safety data will not be replaced, but an analysis of the change from baseline to the last available value under treatment and the minimum and maximum post baseline will be determined for quantitative safety laboratory variables. In general, the last measurement taken between the first intake of randomised trial drug and drug-stop date + 7 days will be analysed as the last value on-treatment.

16.1.9 Documentation of statistical methods

Proprietary confidential information © 2019 Boehringer Ingelheim International GmbH or one or more of its affiliated companies

Boehringer Ingelheim

TSAP for BI Trial No: 1218.102

Page 26 of 47

Proprietary confidential information © 2019 Boehringer Ingelheim International GmbH or one or more of its affiliated companies

Missing dates and times

Missing or partial date and time information for AEs will be replaced according to general BI rules (2).

If the date of first drug administration is missing but the patient was randomised and treated, the date of the first drug administration will be set to the date of randomization. If the date of first administration is partially missing with the month and year present, the day will be set to the date of randomization if randomisation was in the same month. If randomization was in the month prior to the first drug administration the missing day will be imputed as the first day of the month. A missing time of first drug administration will be imputed as 12:00 o'clock noon, missing administration times at on-treatment visits will be imputed by 8:00 o'clock in the morning.

As a general rule, a missing drug stop date will be imputed according to the following principles:

- If an End of Treatment (EoT) visit is documented, it should be the date of the EoT visit.
- If the date is incomplete with only month and year and the EoT visit is missing, it should be the first day of the following month.
- If the patient is lost to follow-up it should be the date of the last visit + the longest treatment duration based on drug supply + 1 day.
- All other cases need to be assessed by the trial team on an individual basis, trying to use the points above as guidance.

Additional rules for the treatment set-up in O*C:

- Since usually no times are available for the start of the screening, placebo run-in period will be considered to start at 0:00 o'clock (midnight).
- Also the start of the post-treatment period will be considered at 0:00 o'clock (midnight) on the day after the study drug stop date.
- The post study period on the date after the follow-up visit, starting at 0:00 o'clock midnight.
- In general, the start of the post-treatment period is defined as date of last drug administration + 1 day. If the drug stop date is incomplete with only month and year present, the post-treatment period starts on the first day of the following month (i.e. at the same day as the imputed drug stop date).
- The post study period start is intended to start on the date of last contact + 1 day and the date of last contact is assumed to be after the date of last drug administration. In patients who discontinue the study, it can happen that the date of last contact is before date of last drug administration. To account for such cases the start of the post-study

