5.2 ASSESSMENT OF EFFICACY

HbA_{1c}

Blood samples for the determination of HbA_{1c} will be taken at all visits except Visit 2. The blood sample can be taken at any time during the visit. For the determination of HbA_{1c}, 3 mL of blood will be collected. The samples will be analysed at a central laboratory or its affiliates having a National Glycohemoglobin Standardization Program (NGSP) Level I certificate. Further details about sample handling, shipment, and assay procedures can be found in the Investigator's Site File (Lab manual).

Fasting plasma glucose (FPG)

Blood samples for the determination of FPG at the central laboratory will be taken after an overnight fast. The samples should be taken before breakfast and before trial drug administration. The samples will be measured at a central laboratory using validated assays. Further details about sample handling and shipment can be found in the ISF (Lab manual).

Meal Tolerance Test (MTT)

Meal Tolerance Test (MTT) will be performed using a standardised breakfast. MTT at Visit 3 would be performed before randomisation, i.e. without intake of trial medication during the MTT.

At Visit 3, after blood sample of FPG drawing, patients would have a standardised breakfast and intake metformin and/ or accepted pre-mixed insulin (if applicable), finished within 15 min, and PPG blood samples would be collected at time points 60 ±10 min and 120 ±10 min after the start of standardised breakfast. Study medication would only be taken after last PPG blood samples drawing, i.e. following randomisation.

At Visit 8, 30 min after blood sample of FPG drawing and administration of study medication, patients would have a standardised breakfast and intake metformin and/ or accepted pre-mixed insulin (if applicable), finished within 15 min, and PPG blood samples would be collected at time points 60 ±10 min and 120 ±10 min after the start of standardised breakfast.

Weight and Waist circumference

Weight measurements should always be done on the same scales for one patient. In order to get comparable body weight values, it should be performed in the following way:

- fasting (except for the screening visit),

- after the urine sampling (weight after bladder voiding),
- shoes and coat/jackets should be taken off
- pockets should be emptied of heavy objects (i.e. keys, coins etc)

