6. INVESTIGATIONAL PLAN

6.1 VISIT SCHEDULE

All trial visits should be routinely scheduled in the morning, at approximately the same time of day (07:00 AM to 11:00 AM). If a patient mistakenly takes trial medication on the morning of a visit before attending the trial site (excluding visits starting before randomisation) or comes in non-fasted where a fasting condition is required (all visits except screening), the visit should be rescheduled for another day as soon as possible reminding the patient about the expected conditions. The rescheduled visit must take place in a short enough time-frame so that the patient has sufficient trial medication available.

All patients are to adhere to the visit schedule as specified in the [Flow Chart](#). If any visit has to be rescheduled, subsequent visits should follow the original visit date schedule. The trial medication packs contain sufficient medication to allow for these time windows.

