6.2.2 Treatment period

The treatment period is from Visit 3 to Visit 8. Patients will be dispensed medication at each of these visits (except for Visit 8). Medication number of each occasion will be allocated by IRT (refer to IRT user manual).

Patients should not take study medication at home on the morning of trial visits during the treatment period.

Randomisation visit (Visit 3)

Visits should be performed fasting and as indicated in the [Flow Chart](#) and the respective protocol sections.

Randomisation/treatment allocation and dispensing of study medication should be the last activity at this visit.

Visits 4-8

Visits should be performed as mentioned in the Flow Chart and the respective protocol sections.

If a patient prematurely discontinues from the 24-week treatment period, the patient must return to the trial site for both Visit 8 (within 7 days of stopping study treatment) and Visit 9 (7 days after Visit 8), which will be performed.

The investigator may initiate any additional antidiabetic therapy for the patient, based on his or her discretion, no sooner than one day after discontinuing study medication or after Visit 8.

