6. GENERAL ANALYSIS DEFINITIONS

6.1 TREATMENT(S)

There will be 5 treatment phases in this trial: screening period, placebo run-in period, double-blind treatment period (with either BI drug or matching placebo), post-treatment and post-study.

Table 6.1: 1 Treatment regimens / study intervals

| Label | Interval | Start date | Start time |
|------------------------|----------------------------------|--|---|
| Screening | Screening period | Date of informed consent | 00:00 |
| Run-in Placebo | Placebo run-in period | Date of first administration of run-in medication | 00:00 |
| Lina 5 mg / Placebo | Double-blind treatment period | Date of first administration of study medication for double-blind treatment period | Time of first administration of study medication, 12:00 if missing |
| Post-treatment | Post-treatment | Date of last drug intake + X* + 1 | 00:00 |
| Post-study | Post-study | Date of last contact + 1 | 00:00 |

* The endpoint specific follow-up period for the assignment to active treatment are presented in detail in [Section 6.7](#).

The purpose of the definition in the above is to describe all the different study/treatment intervals, in which a patient can lie during the course of the trial. Note that the term “treatment regimen” can also cover time periods with no active treatment.

The efficacy and safety analyses will follow the intention-to-treat (ITT) principle in assigning patients to treatment groups, i.e. patients will be analysed as randomised.

If a patient erroneously receives the wrong trial drug, the patient will be analysed ‘as randomised’. Additionally, the AEs with an onset during the time of the incorrect study treatment will also be listed separately.

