6.7 BASELINE, TIME WINDOWS AND CALCULATED VISITS

With regard to efficacy and safety endpoints, the term “baseline” generally refers to the last observed measurement prior to administration of any randomised study medication. For daily insulin dose the baseline will be derived from the eCRF and is equal to the daily insulin dose at day of first study medication intake. Also, for metformin, baseline dose refers to the dose at day of first study medication intake.

Measurements taken prior to the first intake of randomised study drug will be considered pre-treatment values. The pre-treatment values will be assigned to a visit according to the nominal visit number as recorded on the eCRF or as provided by the laboratory.

The date and clock time of the first drug administration will be used to separate pre-treatment from on-treatment values. Measurements taken after the first intake of randomised study drug will be considered on-treatment values if they have been obtained up to end of the parameter specific follow-up period as defined in Table 6.7: 1 below and will be assigned to the randomised study drug for analyse.

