16.1.9 Documentation of statistical methods

Proprietary confidential information © 2019 Boehringer Ingelheim International GmbH or one or more of its affiliated companies

Boehringer Ingelheim

TSAP for BI Trial No: 1218.102

Proprietary confidential information © 2019 Boehringer Ingelheim International GmbH or one or more of its affiliated companies

The midpoint between two on-treatment visits defines the end of a time window, with the midpoint being included in the time window of the preceding visit. The end of the time window of the last on-treatment visit (EoT) is endpoint dependent (cf. [Table 6.7: 1](#)).

Table 6.7: 2 Time windows for on-treatment efficacy measurement scheduled for each on-treatment visit

| Visit number | Visit label | Planned days after randomisation | Planned days on treatment | Time window (actual days on treatment) | |
|--------------|-------------|----------------------------------|---------------------------|--|-------------------------------|
| | | | | Start | End ^A |
| 3 | Baseline | 0 | 1 | NA | 1 ^B |
| 4 | Week 4 | 28 | 29 | 2 | 43 |
| 5 | Week 8 | 56 | 57 | 44 | 71 |
| 6 | Week 12 | 84 | 85 | 72 | 106 |
| 7 | Week 18 | 126 | 127 | 107 | 148 |
| 8 | Week 24/EoT | 168 | 169 | 149 | Study drug stop date + X days |

^A In case of premature discontinuation of the study drug a Visit 8 (EoT) has to be performed. If such a Visit 8 falls into the time window of a previous visit, measurements will be assigned to this previous visit and the visit value will be determined as described below. In this case the time window for the visit that includes Visit 8 will end X days after the study drug stop date, including Day X. The definition of X is endpoint specific, cf. [Table 6.7: 1](#).

^B Only values taken prior to the start of treatment with randomised study drug can be considered baseline values. Time windows will be used for assignment of measurements to scheduled visits.

For examinations that are not planned at every on-treatment visit, the time windows will be defined according to the same algorithm, based on the midpoint between the planned visit day of such an examination.

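### Imputing a missing first-dose time as 12:00 can misclassify a correctly taken Visit 3 two-hour PPG as on-treatment (minor)

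*SAP*

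**What the plan says.** The noon rule appears twice in the SAP. Section 6.6, under missing dates and times, has "A missing time of first drug administration will be imputed as 12:00 o'clock noon". Table 6.1:1 repeats it for the start of the double-blind period: "Time of first administration of study medication, 12:00 if missing".

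SAP 6.7 makes that time operative: "The date and clock time of the first drug administration will be used to separate pre-treatment from on-treatment values". Footnote B to Table 6.7:2 adds "Only values taken prior to the start of treatment with randomised study drug can be considered baseline values". The first on-treatment window in the same table opens on day 2.

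The protocol fixes the order of events at Visit 3. On the meal test, section 5.2 says "Study medication would only be taken after last PPG blood samples drawing, i.e. following randomisation". Section 6.2.2 agrees: "Randomisation/treatment allocation and dispensing of study medication should be the last activity at this visit". PPG samples are due "60 ±10 min and 120 ±10 min after the start of standardised breakfast" (section 5.2). On clock times, section 6.1 says "All trial visits should be routinely scheduled in the morning, at approximately the same time of day (07:00 AM to 11:00 AM").

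**The concern.** The protocol already determines that every Visit 3 PPG sample precedes the first dose. The SAP replaces a missing dose time with a fixed hour that does not respect this order when the meal test runs late. An imputed value can then override what is known about the sequence and turn a valid baseline into an on-treatment value.

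For 2-hour PPG there is no fallback. Protocol 5.2 describes the meal test at Visits 3 and 8 only, and SAP 6.3 admits a patient to the MTT-set only with a valid test at both ends, including a valid 2-hour PPG. The ANCOVA in SAP 7.5.2 runs on that set. The patient would be lost from a named secondary endpoint although the sample was taken as the protocol asks.

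**Working it through.** The plan gives no figure to reproduce. The check is clock arithmetic followed by tracing the rules.

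**Step 1: when can the sample fall after noon?** The 2-hour PPG is drawn at breakfast start plus 110 to 130 minutes (Protocol 5.2).

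| Breakfast start | Sample window | Against 12:00 |
|---|---|---|
| 07:00 | 08:50–09:10 | before |
| 08:00 | 09:50–10:10 | before |
| 09:00 | 10:50–11:10 | before |
| 10:00 | 11:50–12:10 | either side |
| 11:00 | 12:50–13:10 | after |

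The sample can be after noon once breakfast starts later than 12:00 − 130 min = 09:50. It must be after noon once breakfast starts later than 12:00 − 110 min = 10:10.

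**Step 2: what happens to such a sample if the dose time is missing?**
- The dose is set to 12:00, so the sample counts as taken after the first dose.
- Footnote B bars it from being a baseline value.
- It was taken on day 1 and the Week 4 window starts on day 2, so it belongs to no analysis visit.
- The nominal-visit rule in SAP 6.7 covers only values already classed as pre-treatment, so it does not restore the sample.

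If the dose date is missing too, SAP 6.6 sets it to the randomisation date. That is Visit 3 (Protocol 7.6), so the noon rule then applies on the day of the meal test.

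**Step 3: how many patients?** Two inputs are needed and neither is in the documents, so both are assumptions.

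*Share of late samples.* Assume visit starts spread evenly over 07:00–11:00 (240 minutes), a delay d in minutes from arrival to breakfast, and a sample at exactly 120 minutes. Samples fall after noon for visits starting after 10:00 − d, so the share is (60 + d)/240:
- d = 0: 60/240 = 25%
- d = 30: 90/240 = 37.5%
- d = 60: 120/240 = 50%

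*Rate of missing first-dose times, m.* Expected lost baselines = 206 × m × share:

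| m | 25% | 37.5% | 50% |
|---|---|---|---|
| 1% | 0.5 | 0.8 | 1.0 |
| 5% | 2.6 | 3.9 | 5.2 |
| 10% | 5.2 | 7.7 | 10.3 |

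If no times are missing, the loss is zero.

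**Step 4: with the fix.** If Visit 3 samples stay pre-treatment whenever the dose time is missing and the dose date is the Visit 3 date, none is misclassified from this cause at any visit start.

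**The case against.** The strongest reply is that two conditions must coincide and the documents guard against the first. Protocol 4.1.4 has patients dosed at the site on visit days with the time entered in the eCRF, and section 7.6 requires queries to be resolved before unblinding. This stands: missing first-dose times should be uncommon.

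Second, noon is not an arbitrary choice. SAP 6.6 uses 08:00 for missing times at later visits, and the later default for the first dose does keep most morning Visit 3 samples pre-dose. The 07:00–11:00 range might also describe the whole visit rather than its start, and a long fasting visit is likely to begin early. This stands in part. The protocol speaks of routine scheduling and sets no end time, so a late breakfast is allowed, but an even spread of starts is only an assumption.

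Third, Protocol 7.5 leaves other exceptional cases to be settled before unblinding, and some SAP text was not available for this review, so a rule elsewhere cannot be ruled out. A general clause of this kind is weaker than a stated rule, and no available text corrects the noon rule.

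A reader might also infer a threat to the primary endpoint. Protocol 5.2 lets HbA1c be drawn at any time during the visit, so a late draw could be reclassified, baseline could revert to Visit 1, and the day-1 value could count towards FAS entry. The documents do not support this as a material risk. Fasting blood is taken before breakfast at the same visit, so a post-noon HbA1c would need a separate late draw. A patient who entered the FAS only through a day-1 value would have no HbA1c in any analysis window and would add nothing to the MMRM.

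**Conclusion.** The inconsistency is real: in a foreseeable case the SAP's imputation contradicts the protocol's fixed Visit 3 order and discards a valid baseline. It takes both a missing first-dose time and a breakfast starting later than about 09:50.

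The likely size is small. The 25% to 50% shares apply only to patients whose dose time is missing. They should not be read as a share of the trial, and they rest on an assumed spread of visit starts and breakfast delays. The number affected cannot be derived from the documents.

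Nothing suggests that the loss would differ by arm, since the trial is double-blind and the trigger is a recording gap combined with visit timing. The expected cost is therefore some precision, not bias. It falls on 2-hour PPG, which Protocol 7.3.2 treats as exploratory with nominal p-values. There is no material risk to the primary HbA1c analysis. Minor priority.

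**What to change.** In SAP 6.6 and Table 6.1:1, add: if the time of the first randomised dose is missing and its date, recorded or imputed, is the Visit 3 date, all nominal Visit 3 samples are treated as pre-treatment. Setting the dose time just after the last Visit 3 sample is equivalent. Keep 12:00 only for a first dose on a later date.

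This costs one sentence and one line of derivation code. It needs no new data and changes nothing for patients with a recorded dose time. Making the change before unblinding also avoids case-by-case decisions on baseline values.
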